<Eliquis>

<B0661120> Safety and effectiveness evaluation of patients with non-valvular atrial fibrillation treated with OACs: Comparison between NOACs and warfarin (CER3)

<Final ver.1.1><20180508>

NON-INTERVENTIONAL (NI) STUDY PROTOCOL

Revision	Effective Date	Summary of Revisions
1.1	2018/5/08	Schedule(Milestone) has been revised

<Eliquis>

<B0661120> Safety and effectiveness evaluation of patients with non-valvular atrial fibrillation treated with OACs: Comparison between NOACs and warfarin (CER3)
<Final ver.1.1><20180508>

Study information

Title	Safety and effectiveness evaluation of patients with non-valvular atrial fibrillation treated with OACs: Comparison between NOACs and warfarin (CER3)
Protocol number	B0661120
Protocol version identifier	1.1
Date of last version of protocol	08MAY2018
EU Post Authorisation Study (PAS) register number	Not applicable (this study is not PASS)
Active substance	B : Blood and blood forming organs B01: Antithrombotic agents B01A : Antithrombotic agents B01AF: Direct factor Xa inhibitors B01AF02: Apixaban
Medicinal product	Eliquis (Apixaban)
Research question and objectives	The research questions are: 1) is there any difference in the risk of major bleeding and composite of ischemic stroke, hemorrhagic stroke or systemic embolism (stroke/SE) between patients treated with warfarin and those treated with one of NOACs (apixaban, dabigatran, edoxaban or rivaroxaban) in OAC naïve NVAF patients who start treatment with OACs. The primary objective is to compare the risk of major bleeding and stroke/SE in warfarin-apixaban matched cohorts, warfarin-dabigatran matched cohorts, warfarin-edoxaban matched cohorts and warfarin-rivaroxaban matched cohorts.
Author	PPD [REDACTED], PPD [REDACTED] PPD [REDACTED]

TABLE OF CONTENTS

1. RESPONSIBLE PARTIES.....	4
2. ABSTRACT.....	4
3. AMENDMENTS AND UPDATES	6
4. MILESTONES.....	6
5. RATIONALE AND BACKGROUND.....	7
6. RESEARCH QUESTION AND OBJECTIVES.....	8
7. RESEARCH METHODS.....	9
7.1. Study design	9
7.2. Setting	9
7.2.1. Inclusion criteria.....	10
7.2.2. Exclusion criteria.....	10
7.3. Variables	10
7.4. Data sources	12
7.5. Study size.....	12
7.6. Data management.....	13
7.7. Data analysis.....	13
7.8. Quality control	13
7.9. Limitations of the research methods.....	13
7.10. Other aspects.....	14
8. PROTECTION OF HUMAN SUBJECTS.....	14
8.1. Patient Information and Consent	14
8.2. Patient withdrawal	14

2. ABSTRACT

Title: Safety and effectiveness evaluation of patients with non-valvular atrial fibrillation treated with OACs: Comparison between NOACs and warfarin (CER3)

Version 1.0, Mar.14, 2018. PIH IM CV/MET Medical Affairs, PPD

Rationale and background: Atrial fibrillation (AF) is characterized by a rapid, irregular heartbeat which can cause blood to pool in the atria and increase the risk of the formation of blood clots. It has been reported that AF affects 0.6% to 1.6% of the general population and up to 14% in cardiovascular clinics in Japan¹⁻³. An anticoagulation therapy is a critical treatment to prevent thromboembolism in non-valvular AF (NVAF) patients. Warfarin, a vitamin K antagonist, is the first oral anticoagulant approved for the treatment for prevention of thromboembolism in Japan in 1962 and it had long been the only oral anticoagulant until the first non-vitamin K antagonist oral anticoagulants (NOACs),

<Eliquis>

<B0661120> Safety and effectiveness evaluation of patients with non-valvular atrial fibrillation treated with OACs: Comparison between NOACs and warfarin (CER3)
<Final ver.1.1><20180508>

dabigatran, was introduced with approval for stroke prevention in NVAF patients in March 2011, followed by rivaroxaban in January 2012, apixaban in December 2012, and edoxaban in September 2014 in Japan. NOACs provide more convenient therapeutic options and have been demonstrated at least equivalent efficacy compared to warfarin in Phase 3 clinical trials⁴⁻⁷. Apixaban is one of the four NOACs marketed in Japan and has been demonstrated superiority versus warfarin in preventing stroke or systemic embolism, caused less bleeding, and resulted in lower mortality in patients with atrial fibrillation in Phase 3 clinical trial⁶. However, its safety and effectiveness remains unknown in real-world clinical practice in Japan. Previously we have shown in the CER1 study⁸ that bleeding risks are also less in real world clinical practice in Japan compared to warfarin but effectiveness, that is, prevention of stroke, has not been evaluated yet. This study will evaluate the risk of stroke/SE as well as the risk of bleeding in the real world settings in Japan in patients with NVAF who initiated any of OACs (apixaban, dabigatran, edoxaban, rivaroxaban, or warfarin).

Research question and objectives: The research questions are: 1) is there any difference in the risk of major bleeding and of a composite of (ischemic and hemorrhagic) stroke/SE between patients treated with warfarin and those treated with one of NOACs (apixaban, dabigatran, edoxaban or rivaroxaban) in OAC naïve NVAF patients who start treatment with OACs.

The primary objective is to compare the risk of major bleeding and composite of (ischemic and hemorrhagic) stroke/SE in warfarin-apixaban cohorts, warfarin-dabigatran cohorts, warfarin-edoxaban cohorts and warfarin-rivaroxaban cohorts.

Study design: This is a retrospective, non-interventional observational study using the database provided by Medical Data Vision Co. Ltd. (MDV Co. Ltd.) (data set from March 1st, 2011 to December 31st, 2017) designed to evaluate the difference in safety (major and any bleeding) and effectiveness (composite of stroke/SE) in the matched cohorts created by using a propensity score matching method or a stabilized IPTW (inverse probability of treatment weighted) method. Comparisons of apixaban *versus* warfarin, dabigatran *versus* warfarin, edoxaban *versus* warfarin and rivaroxaban *versus* warfarin will be performed.

Population: Data from OAC treatment-naïve Japanese patients with NVAF initiating OAC treatment will be used for the analysis. Further information on patient selection, enrollment and follow-up time periods are included in Subsections 7.2 below.

Variables: Index treatment of OACs; outcome measures including major bleeding, any bleeding, stroke/SE and demographic and clinical characteristics of the patients.

Data sources: Medical Data Vision database

Study size: The required number of eligible patients for each cohort is estimated in Subsection 7.5 below and also in the Statistical Analysis Plan (SAP).

<Eliquis>

<B0661120> Safety and effectiveness evaluation of patients with non-valvular atrial fibrillation treated with OACs: Comparison between NOACs and warfarin (CER3)
<Final ver.1.1><20180508>

Data analysis: Detailed methodology for data analysis will be described in the SAP. Baseline patient demographic information will be compared among the warfarin and each NOAC cohorts by appropriate tests (e.g., t-test, Mann Whitney-U test, chi-square test) based on the distribution of the measures. Both propensity score matching (PSM) and stabilized IPTW methods will be used to estimate treatment effects of NOACs compared with warfarin. To estimate hazard ratio and 95% confidence intervals of each NOAC compared with warfarin using univariable Cox proportional hazards models (OAC treatment as a single variable) will be used.

Milestones: Data extraction from MDV database: Mar.19 - Mar.26, 2018; Analysis: Apr.01 - Apr.16, 2018; Manuscript submission: JUL. 30th, 2018.

3. AMENDMENTS AND UPDATES

Amendment number	Date	Substantial or administrative amendment	Protocol section(s) changed	Summary of amendment(s)	Reason

4. MILESTONES

Milestone	Planned date
Start of data collection	15 MAY 2018
End of data collection	21 MAY 2018
Final study report	1 OCT 2018

5. RATIONALE AND BACKGROUND

Atrial fibrillation (AF) is characterized by a rapid, irregular heartbeat which can cause blood to pool in the atria and increase the risk of the formation of blood clots. AF affects 0.6% to 1.6% of the general population and up to 14% in cardiovascular clinics in Japan¹⁻³. AF can be categorized into three main categories based on patient characteristics: lone atrial fibrillation – AF in the absence of overt cardiovascular disease or precipitating illness⁹; non-valvular AF (NVAF) – presence of AF without concurrent rheumatic mitral valve disease or history of mitral valve repair or prosthetic heart valve; and secondary AF-AF that occurs in the setting of acute myocardial infarction (MI), cardiac surgery, pericarditis, myocarditis, hyperthyroidism, pulmonary embolism, pneumonia, or other acute pulmonary disease. Anticoagulation therapy is important to prevent thromboembolism in patients with NVAF. Warfarin, a vitamin K antagonist, is the first oral anticoagulant approved for the treatment and prevention of thromboembolism in Japan in 1962 and it had long been the only oral anticoagulant until the first non-vitamin K antagonist oral anticoagulants (NOACs), dabigatran, was introduced with approval for NVAF treatment in March 2011, followed by rivaroxaban in January 2012, apixaban in December 2012, and edoxaban in September 2014 in Japan.

Although randomized control trials (RCTs) aimed at head-to-head comparison with placebo or a reference drug may provide evidence of safety and efficacy of treatments at the highest level, there are potential limitations derived from a limited number of pre-selected patients and strict patient eligibility criteria with regard to age, comorbidities, and concomitant medications. Accordingly, these studies may not accurately represent what happens when drugs are used in general clinical practice. Recently, in order to overcome the drawbacks of RCTs and corroborate the evidence from RCTs, real-world evaluations of drugs have been conducted. As for anticoagulants, there are some studies that have evaluated safety and effectiveness of NOACs such as apixaban, dabigatran, and rivaroxaban in the real-world setting and the results were similar to those obtained from RCTs⁴⁻⁷. However, these studies are not sufficient, especially for effectiveness evaluation, and real-world data (RWD) specific to each country or region are also required. For example, Asian populations, including Japanese population, are known to be more prone to intracranial hemorrhage when treated with warfarin¹⁰. Japan is a rapidly aging society with a large proportion of the population aged 75 years or older. Unfortunately, there have been few large-scale, real-world studies to investigate safety and effectiveness of NOACs in patients with NVAF receiving NOACs versus warfarin in Japan. The objective of this study is to compare the risk of incidence of stroke and bleeding among patients with NVAF newly prescribed any of NOACs (apixaban, dabigatran, edoxaban or rivaroxaban), versus newly prescribed warfarin using a nation-wide administrative claims database.

<Eliquis>

<B0661120> Safety and effectiveness evaluation of patients with non-valvular atrial fibrillation treated with OACs: Comparison between NOACs and warfarin (CER3)

<Final ver.1.1><20180508>

This retrospective study is conducted voluntarily by Pfizer. This study will not be conducted as post-authorization safety study (PASS) [REDACTED] according to the decision by the business process owner [REDACTED].

6. RESEARCH QUESTION AND OBJECTIVES

The research questions:

1. Are there any differences in the risk of major bleeding and any bleeding between NOACs and warfarin in the general practice settings in Japan?
2. Are there any differences in the risk of stroke/systemic embolism between NOACs and warfarin in the general practice settings in Japan?

The primary objective of the study compare both the risk of stroke/ SE and of bleeding events among patients with NVAF initiating treatment with one of NOACs (apixaban, dabigatran, edoxaban or rivaroxaban) versus warfarin.

The secondary objectives are

1. to compare the risk of major GI bleeding, any GI bleeding, and intracranial Hemorrhage between warfarin-initiators and NOAC-initiators
2. to compare the risk of ischemic stroke, hemorrhagic stroke or SE between warfarin-initiators and NOAC-initiators

CCI

<Eliquis>

<B0661120> Safety and effectiveness evaluation of patients with non-valvular atrial fibrillation treated with OACs: Comparison between NOACs and warfarin (CER3)
<Final ver.1.1><20180508>

7. RESEARCH METHODS

7.1. Study design

This is a retrospective observational study using data from the MDV database (data set from March 1st, 2011 to December 31st, 2017). Among patients registered in the database patients are selected based on the inclusion and exclusion criteria (see blow). The first observed prescription of apixaban, dabigatran, edoxaban, rivaroxaban or warfarin is used to identify the patient's index date (date of the first prescription of any OACs is defined as "index date") and treatment cohort. Study measures include: (1) for safety evaluation: major bleeding and any bleeding; (2) for effectiveness evaluation: a composite of ischemic stroke, hemorrhagic stroke or SE.

The follow-up period is variable, and will begin on the next day of the index date and continue until the earliest of the following scenarios – occurrence of target outcome event (details available in Section 8.2); discontinuation of the index OAC; switching from the index OAC; withdrawal from the database.

7.2. Setting

This study uses data from the MDV database, which includes the data used for both inpatient and outpatient insurance claims by hospitals according to the Diagnosis Procedure Combination (DPC) procedure.

The study population will consist of adults with NVAF who are newly prescribed apixaban, dabigatran, edoxaban, rivaroxaban or warfarin. Follow-up time period starts from the next day of the index date, and ends depending on following outcomes which observed first.

1. Major bleeding when the target outcome for the analysis is major bleeding.
2. Composite of (ischemic or hemorrhagic) stroke and SE when the target outcome for the analysis is the composite endpoint.
3. Any bleeding when the target outcome for the analysis is any bleeding.
4. Discontinuation of the index OAC: The index treatment will be considered to be "discontinued" if the index OAC is not prescribed within 45 days after prescription refill date (calculated from the last refill date plus days of supply) of the index OAC, even though the patient has >1 medical encounter records after more than 45 days following the prescription refill date. The supposed prescription refill date is regarded as the last day of the follow-up for discontinued patients.
5. Switching from the index OAC: The index treatment is regarded as "switched" if non-index OAC is prescribed within 45 days after prescription refill date of the index OAC when the patient has 1> medical encounter records after more than 45 days following the prescription refill date. The switched day is regarded as the last day of the follow-up for the switched patients.

<Eliquis>

<B0661120> Safety and effectiveness evaluation of patients with non-valvular atrial fibrillation treated with

OACs: Comparison between NOACs and warfarin (CER3)

<Final ver.1.1><20180508>

6. Withdrawal from the database: The patients are regarded as “withdrawal” from the database if the index OAC is not prescribed within 45 days after prescription refill date of the index OAC and there is no data of the patient on the database after prescription refill date. The last medical encounter is regard as the last day of the follow-up for patients withdrawn from the database.

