10.1.3 Analysis of Time-to-Event Data

Time-to-endpoints will be summarized by OAC with the number and percentage of patients with event, and event rates. Event rates will be calculated as the number of patients with event per 100 patient-years at risk. In addition, total patient-years will be presented for each OAC.

Patients who experience a clinical endpoint event after the earlier of their discontinuation of the index OAC, switching from the index OAC, withdrawal from the database, or the end of intended follow-up period (i.e., two years after the index date as primary and one year for a sensitive analysis) will be censored.

Patients who do not experience a clinical endpoint event will be censored at the earlier of their discontinuation of the index OAC, switching from the index OAC or withdrawal from the database will be censored.

Propensity score matching

See above

Cox proportional hazards model

Cox proportional hazards model will be used to compare endpoints in each of the propensity-score-matched cohorts, with robust sandwich estimates to account for the clustering within matched sets. The Cox proportional hazards model will include only index OAC treatment as the independent variable if patient characteristics are balanced between groups based on standardized difference in components of the PS. If not balanced, the unbalanced variable will be also included to the model in addition to the index OAC treatment. The hazard ratios with corresponding 95% confidence intervals and p-values will be reported.

CCI

Kaplan-Meier Method

For each endpoint, Kaplan-Meier curves will be plotted for the time from the index date to first event by index OAC treatment in each of the propensity-score-matched cohorts. The log-rank test is used for comparison between two curves.

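### The 31 December 2017 data cut is not named as an end of follow-up, so event-free patients still on treatment end at their last encounter. Rates are slightly overstated, mainly for edoxaban.

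*Protocol*

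**What the plan says.** Protocol 7.1 fixes the data window ("data set from March 1st, 2011 to December 31st, 2017"). Besides the target event, it lists three ends of follow-up: "discontinuation of the index OAC; switching from the index OAC; withdrawal from the database". Protocol 7.2 defines them.

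- **Rule 4, discontinuation.** "The supposed prescription refill date is regarded as the last day of the follow-up for discontinued patients". The supplied period counts as follow-up.
- **Rule 6, withdrawal.** A patient is withdrawn "if the index OAC is not prescribed within 45 days after prescription refill date of the index OAC and there is no data" after the refill date. The end date is set by "The last medical encounter is regard as the last day of the follow-up for patients withdrawn from the database".

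SAP 10.1.3 adds a further limit, "the end of intended follow-up period (i.e., two years after the index date as primary and one year for a sensitive analysis", in its sentence on patients whose event falls after the end of follow-up. Its sentence on patients without an event ends with "switching from the index OAC or withdrawal from the database will be censored" and repeats neither the two-year limit nor the data cut. Event rates are patients with an event per 100 patient-years at risk. Under SAP 8.1 and 8.2, outcomes come from hospital claims.

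**The concern.** Take a patient on treatment whose supply lasts beyond 31 December 2017. Rules 4 and 5 both refer to encounters more than 45 days after the refill date, which the data cannot contain. Rule 6 is what remains: no later prescription and no later record can be seen, so follow-up ends at the last encounter.

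That end date depends on the outcome. If a stroke or bleed occurs between the last routine visit and the cut, the admission is an encounter, and both the event and the time up to it are counted. If nothing happens, the same stretch of treated, observable time is dropped. Numerators stay whole and denominators shrink, so rates are overstated and late Cox risk sets lose event-free patients.

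The loss is proportionally larger where more patients are still in follow-up at the cut. Launch dates make that edoxaban (September 2014), and edoxaban against warfarin is one of the four primary comparisons.

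**Working it through.** **The plan's own figures.** No figure in the documents concerns the data cut. The nearest is the stroke/SE sample-size table in SAP 6.2. Events needed are 4(1.960 + 0.842)²/(ln HR)², and patients per group are events/(p₁ + p₂), with p = 1 − exp(−rate × T). For HR 0.6 and 1.2%/year with T = 2 years: 120.3/(0.0237 + 0.0143) = 3,166, as printed. The other cells agree within 1.2% (for example 3,521 against 3,488, and 6,898 against 6,817). The table therefore assumes two full years of follow-up for everyone.

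**Inputs from the documents.** The data end on 31 December 2017. They start on 1 March 2011 and the look-back is 180 days, so warfarin and dabigatran indexing starts about the end of August 2011. Launches are rivaroxaban January 2012, apixaban December 2012 and edoxaban September 2014 (mid-month used). The cap is two years.

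**Assumptions, not in the documents.** Index dates are uniform over an accrual window of A years. Supply length L is 30, 60 or 90 days, equal across drugs. Refill visits are the only encounters. There is no discontinuation, and the cap applies with or without an event.

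**Formulas.** The share ended by the cut is s = 2/A. Mean person-time is about 2 − 2/A years, ignoring the small loss to events. An affected event-free patient loses L/2 on average. Inflation is s(L/2)/(2 − 2/A − s(L/2)).

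- Warfarin: A = 6.34, s = 31.5%, person-time 1.685 years. At L = 90, the loss is 0.315 × 45/365.25 = 0.0389 years, so inflation is 0.0389/1.646 = 2.4%.
- Edoxaban: A = 3.29, s = 60.7%, person-time 1.393 years. At L = 90, the loss is 0.607 × 45/365.25 = 0.0748 years, so inflation is 0.0748/1.318 = 5.7%.
- Ratio: 1.057/1.024 = 1.032.

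Simulation at 2.1%/year, one of the SAP's four control rates, agrees:

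| Drug | Share ended by cut | Inflation, L = 30/60/90 | Ratio to warfarin |
|---|---|---|---|
| Warfarin, dabigatran | 32% | 0.8/1.5/2.3% | 1.000 |
| Rivaroxaban | 34% | 0.8/1.7/2.5% | at most 1.002 |
| Apixaban | 40% | 1.0/2.0/3.1% | 1.002 to 1.008 |
| Edoxaban | 61% | 1.8/3.7/5.6% | 1.010 to 1.032 |

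**Sensitivity.**

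- *Discontinuation at 30%/year:* edoxaban inflation is 1.7/3.5/5.4% and the ratio 1.010 to 1.030.
- *Other encounters:* with 6 or 12 extra encounters a year (assumed) and L = 90, the mean lost time falls from 45 days to about 29 or 21. The edoxaban/warfarin ratio falls to about 1.02 or 1.013.
- *Unequal spacing:* warfarin at 30 days with edoxaban at 60 to 90 gives 1.03 to 1.05. Warfarin at 90 with edoxaban at 30 gives about 0.995, a reversal.
- *No cap for anyone (Protocol text alone):* warfarin 1.3/2.6/3.9%, edoxaban 2.5/5.2/7.8%.

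**Against precision.** Protocol 7.5 cites 4,438 eligible edoxaban patients in the previous study. At 1.0 to 1.39 patient-years each and 2.1%/year, that is 93 to 130 events per matched arm. The SE of the log hazard ratio, √(2/events), is then 0.147 to 0.124. A shift of 1.010 to 1.032 is 0.010 to 0.0315 on the log scale, about 0.07 to 0.25 SE.

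**The case against.** The strongest reply is that the effect is small and largely contained. The SAP's two-year limit confines it to patients indexed in about the last two years. The last encounter is also not the last refill: the database holds inpatient and outpatient claims, so any other visit at that hospital recovers part of the lost time. Both points stand, which makes the refill-only figures an upper range for equal supply lengths.

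A second reply is that rule 6 needs a 45-day window without a prescription. Where that window runs past the cut the condition cannot be observed, so the text may be silent on these patients. That is a fair reading. It makes the point a gap rather than a wrong rule, but the remedy is the same.

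Three stronger conclusions are tempting and not supported.

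- *Newer drugs in general are penalised.* With the cap and equal supplies, apixaban moves by less than 1%, and rivaroxaban and dabigatran hardly at all.
- *The direction is fixed against edoxaban.* It depends on visit spacing and index-date patterns, and the documents give neither.
- *The primary conclusions are at risk.* The shift is a fraction of one standard error. A true ratio of 0.80 would appear as about 0.81 to 0.83, and an error in that direction understates a benefit of edoxaban.

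**Conclusion.** The point holds as a small, avoidable bias. Neither document names the data cut as an end of follow-up. On a literal reading, rule 6 then makes follow-up depend on the outcome for patients still on treatment at the cut. The sizes in the table rest on the assumptions listed above and should be read as illustrations. The effect bears mainly on absolute rates and on confidence limits that fall close to 1. It is worth correcting because the error is systematic, so more patients do not remove it.

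**What to change.** Amend Protocol 7.2 and SAP 10.1.3 as follows, for patients with and without events alike.

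1. Add an administrative censoring date: 31 December 2017, or the hospital's last data date if earlier.
2. If the supposed refill date falls on or after that date, end follow-up on that date.
3. If the refill date falls before it but the 45-day window crosses it, end follow-up at the refill date, as rule 4 does. Running these patients on to the cut would credit up to 45 days beyond supply and conflict with rule 4.
4. Apply rule 6 only when the full 45-day window lies inside the data period.

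In the same edit, state the two-year limit in the SAP sentence on patients without an event.

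The cost is a few sentences and a date comparison in the program. The downside is that a few patients who truly left just before the cut gain some unobserved days.
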